### 6.2 Eligibility

Each subject will be evaluated by the Investigator to assess his suitability for entry into this study according to the following criteria:

#### 6.2.1 Inclusion Criteria

6.2.1.1 Subject will be older than 18 years of age

6.2.1.2 Subject was diagnosed with renal calculi meeting the following criteria:

- Largest stone measures no more than 2cm on a single diameter and is no less than 0.8cm as defined by X-ray or CT.
- Accumulative stone burden (addition of all stone diameters) is no more than 2.5cm.

6.2.1.3 Subject is a candidate for FURS procedure

6.2.1.4 Subject is willing and has signed the Informed Consent Form

Any of the following will exclude the subject from the study:

#### 6.2.2 Exclusion Criteria

6.2.2.1 Subject has undergone a previous treatment for stones in the same kidney

- 6.2.2.2 Subject requires another, concomitant procedure, other than FURS, to be performed during this treatment session.
- 6.2.2.3 Female subject is pregnant
- 6.2.2.4 Concomitant anticoagulant medication that cannot be suspended during surgery

## 7 Study Procedures

### 7.1 Study duration and timelines

For each subject the duration of the study will be of 1 month. Subjects may remain hospitalized following surgery, based on physician's discretion. Subjects will be followed at the day of their discharge from the hospital. Each subject will return for a follow-up visit at 1 month following the treatment procedure at which time they will have completed their participation in the study.

It is expected that enrollment of all study subjects at the site will occur within 8-10 weeks from study initiation.

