### 3 Study Design

This is a randomized, two arms, prospective, single center study. Subjects will undergo a single flexible ureteroscopic renal surgery (FURS) procedure for a kidney stone as part of this study, using the study device. Follow up visits are scheduled for the day of release from the hospital and at 1 month post procedure. Additional treatment sessions, if required, will be at the discretion of the investigator, as part of the site standard of practice. Additional treatment sessions will not be included in this study.

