### 5 Outcome Measures

#### 5.1 Primary Endpoints

- Procedure time
- Usage of alternative stone extracting devices
- Catheterization time
- Time to hospital discharge
- Stone clearance based on 1 month follow-up imaging data

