## 6 Patient Population

### 6.1 Source and Sample Size

Subjects shall be selected by the physician within his patient population. One (1) site will participate in this study and will treat twenty (20) subjects. Enrolled subjects that did not complete the full course of the study will be discarded from performance analysis if they have not returned for the one month follow-up visits.

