### 7.3.3 Subject randomization

Allocation of the treatment parameters used during the procedure will be performed using study randomized envelopes. The sponsor will provide the site with sealed envelopes containing "stone breaking" or "stone dusting" treatment parameters. Randomization will be divided into two groups of patients (1-10 and 11-20) with randomization ratio of 1:1 in each group. The randomization list will take into consideration additional subjects that will be required to replace subjects that have dropped from the study. If any subject drops out from the study and is replaced by another subject randomization will continue as per the original randomization scheme (this new subject will not receive the randomization of the subject that was replaced).

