#### 7.6.4 Stent placement

A double-J ureter catheter may be introduced, per standard hospital practice.

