### 7.7 Follow - up Regimen

Each subject will be evaluated by the physician post the procedure as per standard of care to assess subject wellness. Subjects will be released from the hospital per the hospital standard practice. Each subject will return one month following the procedure for a follow-up visit to assess stone clearance and subject well-being. Evaluations during each of these visits will be performed as described in Table 1. Additional unscheduled visits or examinations performed that are not part of the standard of care will be recorded in a dedicated Case Report Form (CRF).

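### Time to hospital discharge is a primary endpoint, yet the plan lets someone who knows the assigned laser setting decide it and describes no masking of subject or ward staff

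*Combined protocol and SAP*

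**What the plan says.** Section 5.1 lists "Time to hospital discharge" among five primary endpoints. It gives no order of importance, no starting point for the clock and no criterion for when a subject counts as ready to leave.

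Two passages bear on how long a subject stays:
- Section 7.1: "Subjects may remain hospitalized following surgery, based on physician's discretion".
- Section 7.7: "Subjects will be released from the hospital per the hospital standard practice". The same section says "Each subject will be evaluated by the physician post the procedure as per standard of care to assess subject wellness".

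The design statement in section 3 reads "This is a randomized, two arms, prospective, single center study". It does not mention masking, and neither does any other section of the text available. Section 7.3.3 says "Allocation of the treatment parameters used during the procedure will be performed using study randomized envelopes", and the sponsor supplies these sealed envelopes to the site. Under section 7.6.2 the laser is then set to the allocated range. Both arms use the same laser and fiber and differ in the assigned pulse energy and frequency.

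**The concern.** Length of stay depends on a decision as well as on recovery. If the person deciding knows the arm, an expectation about dusting can shift the endpoint without any difference in recovery. The plan states such an expectation: sections 1.2 and 9.3.3 anticipate shorter procedures with dusting, section 9.3.3 also anticipates fewer procedure complications, and the primary objective is to demonstrate dusting's efficiency.

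The same knowledge can reach the safety data. Section 9.1.3 takes in events that the patient reports and has the investigator judge whether they relate to the device or the procedure. Adverse events are assessed perioperatively, at discharge and at 1 month. The synopsis places randomization during enrollment, so a subject could learn the setting before surgery. No passage prevents this.

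**Working it through.** **Who can know the arm, and who decides release**

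1. The operator knows the arm, because the envelope holds the parameters (7.3.3) and the operator works with them (7.6.2).
2. The person who evaluates the subject afterwards is called the physician (7.7). Section 6.1 uses the same word for the person who recruits: "Subjects shall be selected by the physician within his patient population". There is one site. The text does not say that the discharging physician is the operator, and it does not require a different person.
3. The subject has spinal or general anesthesia (7.5.1). Under spinal anesthesia a subject may be awake and hear the settings called out.
4. The plan names no post-operative task for which ward staff need the laser setting.

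**Illustration of size**

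The plan gives no SD, effect size or power for this endpoint, so there is no figure of its own to reproduce. Inputs:
- 20 subjects (6.1), allocated 1:1 within each of two groups of ten (7.3.3), hence n = 10 per arm.
- Significance at p < 0.05 with a t-test or Mann-Whitney test (8.1). Two-sided testing is assumed, as the plan does not say.
- Assumption: the true effect is zero, and knowledge of the arm shifts mean discharge time by d SD.

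The t-test has 2 × 10 − 2 = 18 degrees of freedom and a critical value of 2.101. Under a shift d the statistic follows a noncentral t distribution with noncentrality d × √(n/2) = d × √5 = 2.236d. The false-positive rate is the probability that it falls beyond ±2.101.

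| Assumed shift d (SD) | Noncentrality | False-positive rate |
|---|---|---|
| 0 | 0 | 5.0% |
| 0.25 | 0.559 | 8.3% |
| 0.5 | 1.118 | 18.5% |
| 0.75 | 1.677 | 35.5% |
| 1.0 | 2.236 | 56.2% |

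Check at d = 0.5 by the normal approximation: Φ(1.118 − 1.960) + Φ(−1.118 − 1.960) = 0.200 + 0.001 = 0.201. This is slightly above the exact 18.5%, as expected with few degrees of freedom.

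In hours, a 0.5 SD shift is 4, 6 or 12 h if the SD of stay is 8, 12 or 24 h (0.5 × each). These SDs are assumptions.

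**The case against.** The strongest reply is that both passages describe usual care. A physician exercises judgement within hospital practice, so sections 7.1 and 7.7 can be read together. That is a fair reading, and a reader who infers an outright contradiction goes too far. What remains is that neither passage gives a criterion, and the plan does not say which statement governs a primary endpoint.

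A second reply is that masking the ward achieves little if the operator orders discharge. This is correct. Withholding the setting from subject and ward protects the subject-reported events, but it protects the discharge endpoint only if the person deciding is also unaware. Masking would also be partial: section 1.2 expects dusting to need less extraction, section 7.6.3 has basket and forceps use recorded, and either that use or the operative notes may hint at the arm.

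A third reply is that the numbers do not show bias. They do not. The shifts are assumed, and the rates apply to the t-test, not to the Mann-Whitney alternative. Nor is the smallest significant observed difference, 2.101 × √(2/10) = 0.94 SD, evidence of bias: it is the threshold for any continuous endpoint with 10 per arm.

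A reader might also infer that ward orders drive catheterization time, another primary endpoint. The documents do not support this. The endpoint is undefined, and the passage on catheters, "A double-J ureter catheter may be introduced, per standard hospital practice", concerns a step of the operation and says nothing about who orders removal.

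**Conclusion.** The point holds in limited form. A primary endpoint rests on a clinical decision without written criteria, no masking is described, and the operator necessarily knows the setting. This leaves an avoidable route for bias into time to discharge and into reported adverse events. The plan should be changed, and the main steps are cheap.

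The size and direction of any bias cannot be derived from the documents. Under the assumptions of a 0.5 SD shift, no true effect, 10 per arm and a two-sided t-test, the false-positive rate would be about 18.5% instead of 5%; at 0.25 SD it would be 8.3%.

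A reader might go further and call the trial open-label, or say that the operator will decide discharge. The documents state neither: the absence of masking is read from silence, and the identity of the discharging physician is left open.

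**What to change.** 1. Reconcile sections 7.1 and 7.7 into one statement of what governs release, applied identically in both arms. Its content is for the clinical team.
2. State that the allocated setting is recorded only on the Randomization and Treatment forms already listed in section 10.5. It is not announced in the operating room when the subject is awake, and is not disclosed to the subject or ward staff until the 1-month visit is complete. It is disclosed at once on clinical need.
3. Where existing staff allow, have discharge decided by a clinician unaware of the setting. Otherwise, record the time at which discharge-readiness criteria, prespecified by the clinical team, are met, and analyse that time alongside actual discharge.

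**Cost.** Protocol, consent and chart-handling wording, plus one recorded time if the second option in step 3 is used. No extra subjects or visits are needed, and step 3 asks for an unaware clinician only where one is already available. The downside is that the setting stays out of the ward chart for about a month and that masking is only partial. If the deciding clinician is truly unaware of the arm, the shift from this source is zero and the test returns to its 5% rate. With readiness criteria applied by someone who knows the arm, the room for influence is reduced but not removed.

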### 7.2 Study Measures

- Various assessments will be performed throughout the study at different time-points as detailed in Intraoperative Complications – based on Modified Clavien Classification

Table 1.

#### 7.2.1 Objective Measures

- 7.2.1.1 Blood workup: including CBC & BMP
- 7.2.1.2 Urine workup: including urine analysis and urine culture (if applicable)
- 7.2.1.3 Renal stone size and location will be performed using Computer Tomography
- 7.2.1.4 All imaging verifying the diagnosis, pre-intervention images, intra-operative (during laser activation) images, immediate post-operative and follow-up images and relevant fluoroscopy and CT images will be recorded on electronic media for documentation, further analysis and data recording.  
Subject anonymity will be assured for all images by deleting any ID detail. Only the code for the Case Number in the study will appear on the records being transferred to the sponsor.
- 7.2.1.5 Stone clearance status will be confirmed one month post discharge using non contrast abdominal Computed tomography (for Radiolucent calculus) or KUB X-ray combined with kidneys and bladder Ultrasound imaging (for radiopaque calculus).

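### Section 7.2.1.5 dates the stone-clearance image from discharge, while every other section that names a starting point for that visit counts from the procedure

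*Combined protocol and SAP*

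**What the plan says.** Two primary endpoints in section 5.1 are involved: "Stone clearance based on 1 month follow-up imaging data" and "Time to hospital discharge". The clearance endpoint gives an interval of one month but not the event from which it is counted.

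Four places do name that event:

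- Section 7.2.1, item 7.2.1.5, which also sets the imaging modality: "Stone clearance status will be confirmed one month post discharge using non contrast abdominal Computed tomography".
- Section 3: "Follow up visits are scheduled for the day of release from the hospital and at 1 month post procedure".
- Section 7.1: "Each subject will return for a follow-up visit at 1 month following the treatment procedure", followed by "at which time they will have completed their participation in the study".
- Section 7.7: "Each subject will return one month following the procedure for a follow-up visit to assess stone clearance and subject well-being".

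The synopsis, section 6.1, Table 1 and Appendix I refer only to a one-month follow-up. No visit window is given anywhere. On length of stay, 7.1 leaves continued hospitalization to the physician and 7.7 refers to the hospital's standard practice. Neither gives an expected duration.

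**The concern.** Section 7.7 says that the post-procedure visit is the one at which clearance is assessed, so 7.2.1.5 and 7.7 give different dates for the same assessment. For a subject discharged on the day of surgery the two dates agree. For anyone who stays longer they do not, and the date in 7.2.1.5 falls after the visit that 7.1 treats as the end of participation.

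The statistical issue is what the image date depends on. The procedure date is a common origin for both arms. The discharge date is a post-randomization outcome on which the arms are themselves compared. Under 7.2.1.5, an arm with longer stays would be imaged later after surgery. If residual fragments continue to pass during follow-up, that arm would have had more time to clear. Section 1.1 describes dust as washing out spontaneously, which makes such a dependence on time plausible, although the documents do not state it.

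**Working it through.** **Wording.** The plan states no figure on this point, so the first check is a comparison of the places that date the assessment.

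| Place | Counted from |
|---|---|
| 7.2.1.5 | discharge |
| 3 | procedure |
| 7.1 | procedure |
| 7.7 | procedure |
| Synopsis, 5.1, 6.1, Table 1, Appendix I | not stated |

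Three of the four places that name a starting point agree, and 7.2.1.5 is the exception.

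**Shift in timing.** Taking a month as 30 days (assumption), the image day after surgery is 30 under sections 3, 7.1 and 7.7, and 30 + length of stay under 7.2.1.5. The between-arm difference in mean imaging time is therefore 0 by design in the first case and equals the between-arm difference in mean stay, *d*, in the second.

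**Possible effect on clearance.** Inputs from the documents: 20 subjects (section 6.1), allocated 1:1 (section 7.3.3), so 10 per arm; significance level 0.05 (section 8.1), taken as two-sided because sidedness is not stated. Assumed inputs: *d* from 0.5 to 5 days; true 30-day clearance *p* of 50%, 70% or 90% in both arms; and a constant clearance rate, p(t) = 1 − exp(−λt). The arm imaged *d* days later then shows

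q = 1 − (1 − p)^((30 + d)/30).

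Example: p = 0.70, d = 5 gives q = 1 − 0.30^(35/30) = 0.7545, a spurious difference of 5.45 points.

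The chance of a significant result in that direction, by a normal approximation for two proportions (8.1 names tests only for continuous variables), with p̄ = (p + q)/2, is

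Φ( [ (q − p) − 1.96·√(2p̄(1 − p̄)/10) ] / √([p(1 − p) + q(1 − q)]/10) ).

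For the same example: (0.0545 − 1.96 × 0.1992)/0.1988 = −1.69, so Φ = 0.046.

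| *d* (days) | Share of 30 days | Spurious difference, points (range over *p*) | Chance of significance in that direction |
|---|---|---|---|
| 0.5 | 1.7% | 0.38–0.60 | 0.027 |
| 1 | 3.3% | 0.74–1.18 | 0.028–0.029 |
| 2 | 6.7% | 1.42–2.31 | 0.032 |
| 3 | 10.0% | 2.06–3.40 | 0.035–0.037 |
| 5 | 16.7% | 3.19–5.46 | 0.043–0.046 |

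With no shift the last column would be 0.025.

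**Sampling error for comparison.** The standard error of a difference between two arms of 10 is √(2p(1 − p)/10): 22.4 points at p = 0.5, 20.5 at 0.7 and 13.4 at 0.9. The largest spurious difference in the table is about a quarter of the corresponding standard error (5.46/22.4 = 0.24; 5.45/20.5 = 0.27; 3.19/13.4 = 0.24).

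**The case against.** The best defense is that 7.2.1.5 contains a slip and the rest of the plan shows what was meant. Section 7.2 sends the reader to Table 1 for time-points, Table 1 puts the image in the one-month follow-up column, and 7.7 defines that visit as one month after the procedure. Only one visit is scheduled after discharge. The background in section 1.1 also describes the earlier dusting work as reporting clearance one month after the procedure. Much of 7.2.1.5 concerns modality, and nothing shows that the sponsor chose a discharge origin on purpose.

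This stands as an account of probable intent, and it tells against a reader who infers that the endpoint is in fact tied to discharge. That follows only if 7.2.1.5 is the instruction applied. It does not make the conflict harmless: 7.2.1.5 is the item that specifies how clearance is imaged, and no section says which wording prevails.

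A reader might also infer a sizeable bias between arms from long, complicated stays. An assumed stay of 7 or 10 days would give that subject 7/30 = 23% or 10/30 = 33% more time. That is extra time for one person; it is neither extra clearance nor a difference between arms. The documents give no stay data and predict longer stays in neither arm, so they support no direction of bias.

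Finally, imaging after the end of participation could be read as a separate defect. Section 7.1 ties completion to the visit itself, so this is the same mismatch seen from another side.

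**Conclusion.** The contradiction is certain: one primary endpoint has two incompatible dates for any subject who stays beyond the day of surgery. The consequence is conditional. If 7.2.1.5 is applied, the timing of clearance depends on time to discharge, and the arms are imaged at different times since surgery by whatever amount their stays differ. On the assumed inputs (differences in stay of 0.5 to 5 days, constant clearance rate, 30-day clearance of 50% to 90%) this yields about 0.4 to 5.5 percentage points, and raises the chance of a significant result in that direction from 0.025 to at most 0.046. That is small beside sampling error in a trial of this size. The point should be corrected because it concerns a primary endpoint and is nearly free to put right; the documents do not show that the result would be materially biased.

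**What to change.** In 7.2.1.5, change the origin of the one-month interval from discharge to the procedure, in line with sections 3, 7.1 and 7.7. Record the date of the clearance image, derive the days from procedure to image, and report that interval by arm next to the clearance result, so that any imbalance is visible.

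If the sponsor adds a visit window, count it from the procedure date. Its width is for the sponsor to set, bearing in mind that a wide window would not by itself control a shift of a few days, which is why the recorded interval matters.

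The cost is one phrase in the protocol, one derived variable and one line in a results table. No visit or image is added.

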#### 7.2.2 Investigator Subjective Assessments

- 7.2.2.1 Procedure Questionnaire will record subjective usability parameters such as ability to maintain fiber durability and deflection, retropulsion and visibility impairment and resolution (due to bleeding or other disturbances), subjective assessment of lithotripsy efficiency, aspiration and combined procedures.

- Intraoperative Complications – based on Modified Clavien Classification

Table 1 – Assessments time-points

Assessment	Performed During Visit			
	Baseline (Pre-operative)	Perioperative	Hospital discharge	1 month follow- up
Subject assessment (ICF, medical history, demographics, inclusion/exclusion evaluation)	X			
Imaging	X (CT and / or X-ray)			X (CT and / or X-ray)
Blood analysis (CBC & BMP) and urine analysis	X		X	X
Urine culture (if applicable)	X			X
Physician Subjective Procedure questionnaire		X		
Adverse Event Assessment		X	X	X

## 7.3 Screening Procedures

### 7.3.1 Subject Enrollment

1. During the first visit, the investigator will screen the subject for eligibility to participate in the clinical study using the Inclusion, Exclusion criteria. During screening, the study physician will review the subject's medical history to ensure that the subject meets the study criteria.
2. If the subject has met the preliminary study eligibility criteria, the study physician will obtain an informed consent from the subject, clearly indicating his/her understanding of the procedure, requirements and risks involved with study participation and other applicable treatment options.
3. The subject will be enrolled to the study and the treatment will be scheduled.

### 7.3.2 Subject Identification

At enrollment, each subject will receive an identifying number that will include a consecutive serial number. The subject identification number and the subject initials will be used to identify the subject during the entire study and will be entered in the subject's CRF for each treatment and photographs.

### 7.3.3 Subject randomization

Allocation of the treatment parameters used during the procedure will be performed using study randomized envelopes. The sponsor will provide the site with sealed envelopes containing "stone breaking" or "stone dusting" treatment parameters. Randomization will be divided into two groups of patients (1-10 and 11-20) with randomization ratio of 1:1 in each group. The randomization list will take into consideration additional subjects that will be required to replace subjects that have dropped from the study. If any subject drops out from the study and is replaced by another subject randomization will continue as per the original randomization scheme (this new subject will not receive the randomization of the subject that was replaced).

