## Study Synopsis

Study Title	Utilizing Holmium Laser for FURS Renal Stone Lithotripsy Comparing Stone Breaking vs. Stone Dusting Settings	
Protocol No:	LUM-SBU-VP-15-01	
Device Name:	Lumenis Pulse 120H Holmium Laser system	
Design	Prospective, randomized, single center	
Planned Study period	Initiation: January 2016	Final Report: May 2016
Objective	Primary: Demonstrate the efficiency of stone dusting Vs stone breaking of the P120H holmium laser and 200 DFL ball tip fibers Secondary: Demonstrate the usability and safety of stone dusting	
Study population	Twenty (20) subjects presenting with a renal stone and candidates for FURS	
Main Inclusion Criteria	

Subject will be older than 18 years of age

Subject was diagnosed with renal calculi between 0.8 to 2 cm in size

Subject is a candidate for FURS procedure

Subject is willing and has signed the Informed Consent Form

	
Main Exclusion Criteria	

Underwent previous PCNL or FURS in current kidney

Need to perform concomitant procedure, other than FURS

	
Investigational Treatment and study course	
A single FURS procedure will be performed with either high or low frequency holmium laser lithotripsy. Subjects will be randomized during enrollment to receive treatment with one of the two parameter sets.
 
Follow up sessions:
 

Day of discharge

One month follow-up

	
Criteria for Evaluation (endpoints)	
Primary Endpoints:
 

Procedure time

Usage of alternative stone extracting devices

Catheterization time

Time to hospital discharge

Stone clearance based on 1 month follow-up imaging data

 
Secondary Endpoints:
 

Intraoperative Complications – based on Modified Clavien Classification

Visibility during procedure

Occurrence of retropulsion that interferes with procedure

Ability to reach fragments during the procedure

Fiber flexibility with scope deflection- any damage to fiber

Fiber durability- deflection without losing energy/ efficiency

Damage to scope

	

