#### 7.6.2 Lithotripsy

Lithotripsy will be performed using the Lumenis Pulse 120H holmium laser system and the 200 DFL ball tip fiber using the suggested parameter range sets listed below. The treatment set used will be predefined according to the treatment group the subject was randomized to.

Task	Group I (stone breaking)	Group II (stone dusting)
Energy per pulse	1 - 2.0 J	0.2 - 0.5 J
Frequency	10 – 30 Hz	70 – 80 Hz
Maximum power possible	40 W*	40 W*

- Do not exceed the maximum 40W energy

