## 10.10 Modification of Protocol

The protocol may be amended with the agreement of the sponsor and upon notification of and approval by the IRB / EC.

Investigators should review the contents of this protocol. Subsequent alterations should only be made in writing in conjunction with the sponsor.

Medically significant amendments to the protocol (e.g., changes that increase the risk or the inconveniences for the patient, inclusion of new categories of patients, significant modifications to the study device, etc.) must be approved by the local IRB / EC prior to implementation and authorized representative, as applicable.

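### Section 7.3.3 tells the recruiting site the block boundaries, so 2 or more of the 20 allocations are certain in advance and about 13 can be guessed, against 10 by chance

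*Combined protocol and SAP*

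**What the plan says.** Section 7.3.3 sets out the allocation scheme: "Randomization will be divided into two groups of patients (1-10 and 11-20) with randomization ratio of 1:1 in each group". The sponsor supplies sealed envelopes to the site. If a subject is replaced, the sequence carries on, so dropouts do not disturb the two blocks.

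Other sections show who can see and use this:

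- Section 6.1, on size and setting: "One (1) site will participate in this study and will treat twenty (20) subjects".
- Section 6.1, on recruitment: "Subjects shall be selected by the physician within his patient population".
- Synopsis, on timing: "Subjects will be randomized during enrollment to receive treatment with one of the two parameter sets".
- Section 7.6.2, on delivery: "The treatment set used will be predefined according to the treatment group the subject was randomized to". The two arms use different pulse energies and frequencies, so the operator cannot be unaware of the arm.
- Section 10.10, on access to the protocol: "Investigators should review the contents of this protocol". Section 10.1 has the principal investigator sign it.

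Section 7.3.2 gives consecutive serial numbers, so the position within a block is always known. No section withholds the block structure from the site. None requires opaque or sequentially numbered envelopes, or eligibility to be fixed before an envelope is opened.

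**The concern.** Sealed envelopes stop a decision being changed after the allocation is seen. They do not stop the next allocation being predicted from past ones, and printing the boundaries makes some predictions exact. The prediction can be made before a patient is approached, so taking consent first does not remove it.

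Case difficulty can be known at that moment too. Section 7.4 accepts imaging done before enrolment as baseline, and the protocol does not ask for consecutive enrolment. Section 6.2.1 allows a largest stone of 0.8 to 2 cm and a total burden of up to 2.5 cm. Stone burden plausibly affects procedure time and clearance, both listed as primary endpoints. Section 8.1 compares continuous variables by t-test or Mann-Whitney test without adjusting for stone burden, so any imbalance created at selection would pass into the comparison.

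**Working it through.** **Inputs.** 20 subjects at one site (6.1). Two groups of 10 at 1:1 (7.3.3), read as 5:5, so m = 5 per arm per block. The plan gives no effect size or power to reproduce. The only check on its figures is that 2 × 10 = 20, or 10 per arm, which is consistent.

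**1. Certain allocations.** An allocation is certain once one arm's 5 places in the block are used. The expected number per block is 2m/(m+1) = 10/6 = 1.67, so 3.33 over two blocks. Enumerating all C(10,5) = 252 sequences gives 1, 2, 3, 4 or 5 certain places in a block with probability 55.6%, 27.8%, 11.9%, 4.0% and 0.8%. Over both blocks the minimum is 2. Exactly 2 has probability 0.556² = 30.9%, at least 3 has 69.1%, and at least 4 has 38.3%.

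**2. Guessable allocations.** The guesser names the arm with more places left and tosses a coin at a tie. Expected correct per block is m + 2^(2m−1)/C(2m,m) − 1/2 = 5 + 512/252 − 0.5 = 6.53. Over two blocks this is 13.06 of 20 (65.3%), an excess of 3.06 over chance. On average 7.7 of 20 can be called with probability of at least 2/3, certain ones included.

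**3. Possible bias.** Assume each guess moves the chosen case by d SD of difficulty, easier for one arm and harder for the other. The expected difference between arms is 2 × d × (2 × 0.653 − 1) = 0.613d. The documents give no value for d, so a range is shown. The standard error of a difference with 10 per arm is √(2/10) = 0.447 SD. The last column is the two-sided 5% t-test (noncentral t, 18 df) if difficulty carried over fully into outcome, which is an upper bound.

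| d (assumed) | Difficulty difference | In standard errors | Type I error, upper bound |
|---|---|---|---|
| 0.10 | 0.06 SD | 0.14 | 5.2% |
| 0.25 | 0.15 SD | 0.34 | 6.2% |
| 0.50 | 0.31 SD | 0.69 | 9.9% |

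**4. Alternatives for 20 subjects.**

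| Scheme | Correct guesses | Certain or forced if the structure is known |
|---|---|---|
| Current: two blocks of 10 | 13.06 | 3.33 |
| One list of 20, 10:10 | 10 + 2^19/C(20,10) − 0.5 = 12.34 | 20/11 = 1.82 |
| One list of 24, 12:12, first 20 used | 11.45 | 0.06 |
| Maximum imbalance 3 | 11.44 | 2.89 |
| Maximum imbalance 4 | 10.88 | 1.75 |
| Hidden blocks of 2/4/6 (simulated) | 13.93 | none predictable with certainty while hidden |
| Simple randomization | 10.00 | 0 |

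The list of 24 is only an illustration, since the protocol does not say how many replacement envelopes there are. Its guess figure is the sum over k = 0 to 19 of E[max(places left in either arm)]/(24 − k), with hypergeometric counts. Simple randomization carries an 11.5% chance of a 14:6 split or worse.

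**The case against.** Several points can be made for the plan.

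- **The guess rate comes from the blocking, not from the disclosure.** This stands. Someone who only tracks the running imbalance also gets 13.06. Disclosure adds the certainty, so deleting the sentence without regenerating the list would be half a fix.
- **Varied block lengths, the usual remedy, may do harm.** This stands. Hidden blocks of 2/4/6 raise correct guesses to 13.9, 4/6/8 give 13.4, and 6/8/10 give 13.0, which is no real gain.
- **The bias is small and rests on an assumption.** This stands. At d = 0.25 it is about a third of a standard error, in difficulty rather than outcome.
- **The plan already has safeguards.** This stands in part. The sponsor supplies the sealed envelopes. Filling 20 places in 8 to 10 weeks (7.1) limits freedom to pick and delay. Baseline data are summarized (8.1), so gross imbalance would show, but a table with 10 per arm could not reliably reveal modest steering.
- **The 1:1 ratio could mean simple randomization.** That would remove the problem, but tying the ratio to numbered groups points to a fixed 5:5 split.

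A reader might also infer that the protocol names the recruiter as the operating surgeon. It does not. With one site, physician-selected patients and arm-specific settings, that is a strong inference only. Section 7.3.3 does not say when the envelope is opened either. If that were only at surgery, with several enrolled subjects waiting, less would be known at selection, but the Synopsis places randomization at enrolment.

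**Conclusion.** The concern holds as a weakness that is cheap to remove. Under the 5:5 reading, with past allocations known, at least 2 and on average 3.3 of 20 allocations are certain beforehand. About 13 can be guessed correctly, only about 3 more than by chance. It would be too strong to say that most allocations are known, or that the comparison is biased by a given amount. Nothing in the documents shows that steering would occur. The range of 0.06 to 0.31 SD in case difficulty follows only from the assumed shift of 0.1 to 0.5 SD per guess, and the effect on procedure time would be smaller in proportion to how closely difficulty and time are related.

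**What to change.** In 7.3.3, delete the group boundaries. State only that allocation is 1:1 from a sponsor-held list whose structure is not disclosed to the site. Keep the scheme in a separate sponsor document and regenerate the list in one of two ways:

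- one list longer than 20 that includes the replacement envelopes, because an exact 10:10 list of 20 would have its length deduced from the stated sample size; or
- a maximum-imbalance rule, with the limit also undisclosed.

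Do not use small varied blocks. Require opaque, sequentially numbered envelopes, each opened only after eligibility and consent have been recorded.

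The cost is one edited paragraph and one new list. Exact 5:5 balance at the interim and 10:10 at the end would no longer be guaranteed. With a 12:12 list of 24 and four envelopes unused, for example, the final split could be anything from 8:12 to 12:8. The interim in 8.2 states no rule that needs exact balance.
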